1.3. Study description

This study was sponsored by Federal state budgetary institution “Russian scientific center for traumatology and orthopedics” n.a. acad. G.A. Ilizarov” of the Ministry of Health of Russian Federation. The study will take place at this center.

[figure not shown]
It is expected to enroll 70 patients aged 10-18 years with NMD, all of whom will be subjected to thoracic and lumbar spinal deformity surgery.

Patients will be divided into two groups depending on skeletal maturity. The degree of skeletal maturity will be determined on the basis of an X-ray study of spinal and pelvic bones. The type of surgical correction will depend on the group.

[figure not shown]

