3.2. Endpoints

The primary endpoint is decrease in spine deformity grade by 1 or more (according to Chaklin classification) with stabilization or improvement in lung parameters in 12 months after the surgery.

Secondary endpoints are as follows:

1. Hospitalization by all causes
2. Improvement in life quality after surgery according to scales (VAS, GMFCS, RLAS, FIM, MACS) in 6 months and 12 months after surgery.

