3.3. Study design

This study is prospective, non-randomized, single-center, open and non-comparative; it involves two parallel groups of patients (children aged 10-18 years) with severe thoracic and lumbar spinal deformities at NMD.

Patients are divided into groups depending on skeletal maturity determined on the basis of an X-ray study of spinal and pelvic bones. The type of surgical correction will depend on the group.

1. Group of patients with spinal deformities corrected and stabilized with bilateral connector systems (growing skeleton).

Bone maturity grades I-III (Sadofyeva classification) or I-II (Risser classification).

Bilateral connector systems (“growing rods”) will be used in this group (N = 30).

2. Group of patients with spinal deformities corrected and stabilized with bilateral multiple fixation points (mature skeleton).

Bone maturity grades IV-V (Sadofyeva classification) or III-IV (Risser classification).

Inside this group (N=40) two subgroups are planned depending on varying anatomic characteristics thus allowing for specific treatment option:

- *Subgroup 1 – segmental fixation*
- *Subgroup 2 – intermittent (next nearest) segment fixation*

Patients will be enrolled in study groups in consecutive stages, according to enrollment criteria described above

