3.7. Data collection

Clinical data will be collected at certain time points of this study. The requirements to data collection and study visit schedule are given in table 1.

Table 1: Study stages and procedures

Stages / Procedures	Screening	Distribution into groups and surgery	Postoperative period (early observation: 24-48 hours)	Before discharge (ca. after 21 days)	6 months post operation ± 14 days	12 months post operation ± 30 days
	Visit No. 1	Visit No. 2	Visit No. 3	Visit No. 4	Visit No. 5	Visit No. 6
Informed consent	X					
Anamnesis morbi	X					
Physical examination, evaluation of orthopedic, somatic and neurological status	X	X	X	X	X	X
Evaluation of quality of life (GMFCS, RLAS, FIM, MACS)	X				X	X
X-ray ¹	X			X	X	X
Intraoperative control efficacy evaluation		X				

CHILDren with neuromuscular diseases – efficacy eVALuation of spinal deformity surgeRY via different pedicle screw fixation systems study
CHIVALRY study

Clinical blood analysis ²	X		X	X		X*
Biochemical blood analysis ³	X		X			X*
Spirometry*	X					X*
EchoCG*	X					X
CT ⁴	X			X		X**
MRI ⁵	X					
Documentation of serious adverse events		X	X	X	X	X

1. Spinal X-ray (from Th1 to S4), 2 standard projections.
2. RBC, hematocrit, hemoglobin, WBC, thrombocytes, ESR.
3. Total protein, creatinine, urea, bilirubin, AST/ALT, glucose.
4. Spine CT (from Th1 to S4).
5. MRI of the spine and the spinal cord.

* Performing research only for medical reasons;

** If there are signs of a bone block in the area of instrumental fixation according to the radiograph of the spine

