3.8.5. Visit No. 4. Before discharge (ca. after 21 days)

The duration of inpatient stay is determined by standards of the healthcare institution and on the average amounts to 21 days (depending on the patient's clinical condition). The following study procedures will be performed before discharge:

- Physical examination;
- Spine X-ray: scoliotic and kyphotic deformity measurements (Cobb angle), static and dynamic imbalance in frontal and sagittal planes;
- Spine CT and verification of screw position;
- laboratory tests (clinical blood analysis, blood chemistry);
- documentation of serious adverse events.

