3.8.7. Visit No. 6. 12 months after the procedure

The following study procedures will be performed during a scheduled visit 12 months after the procedure:

- physical examination and clinical evaluation: physical status (body mass index);
- functional status and life quality (with VAS, FIM, MACS, GMFCS);
- spine X-ray: scoliotic and kyphotic deformity measurements (Cobb angle), static and dynamic imbalance in frontal and sagittal planes;
- laboratory tests (clinical blood analysis) (as an option if there is a medical condition);
- spirometry, ECG, echocardiography (as an option if there is a medical condition);
- Spine CT with evaluation of screw position and fusion mass (as an option, if there are signs of a bone block in the area of instrumental fixation according to radiographs of the spine);
- documentation of serious adverse events.

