6. STATISTICAL ANALYSIS AND METHODS

Primary and additional quantitative efficacy and safety criteria will be summarized in shift tables and presented by means of descriptive statistics; the appropriate methods will be selected depending on the data. Missing data will be indicated as N/A and not considered in aggregate statistics. The significance of differences between data groups will be evaluated using the criteria depending on the number of observations and distribution type of parameter values within groups. Software: Statistical Package for the Social Sciences (SPSS), v. 22.0 (SPSS Inc., Chicago, IL, USA). T-criteria: 1) comparison of correction of sagittal and frontal spinal deformity components with graded FC parameters. Differences will be considered significant if two-sided $p < 0.05$.

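### The 12-month CT is taken only where the X-ray suggests fusion, so any CT fusion rate among scanned patients would overstate fusion in all operated patients

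*Combined protocol and SAP*

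**What the plan says.** The Visit 6 list in section 3.8.7 includes "Spine CT with evaluation of screw position and fusion mass". It marks this as optional and attaches a condition: "if there are signs of a bone block in the area of instrumental fixation according to radiographs of the spine". The double-asterisk footnote to Table 1 (section 3.7) repeats the condition for the 12-month CT: "If there are signs of a bone block in the area of instrumental fixation according to the radiograph of the spine". The visit text and the table therefore agree, and the condition is not a stray phrase.

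The CT before discharge carries no such condition. Section 3.8.5 lists "Spine CT and verification of screw position" and does not mention fusion mass. Table 1 schedules the Visit 6 X-ray without a condition. Section 3.8.7 describes that X-ray as measuring Cobb angle and imbalance and does not ask for a fusion reading.

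On missing values, section 6 states: "Missing data will be indicated as N/A and not considered in aggregate statistics". It gives no denominator for CT findings and no correction for selective scanning.

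Section 3.2 contains no CT outcome. It begins "The primary endpoint is decrease in spine deformity grade by 1 or more (according to Chaklin classification" and adds lung parameters at 12 months. The secondary endpoints are hospitalization and the functional and quality-of-life scales.

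**The concern.** The sign that triggers the CT is a sign of the thing the CT is meant to assess. Patients whose X-ray shows no bone block have no scheduled 12-month CT, and non-fusion would be expected to be concentrated among them. If their absent results are dropped as N/A, the remaining CT fusion rate comes from a favourably selected subset. This is verification bias.

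What is at stake is descriptive. A reader of the final report could take a CT fusion percentage as applying to every operated child. It could also be used as evidence for the surgical planning algorithm in section 3.1, which covers the number and location of fixation points. Section 6 foresees tests between groups, so a comparison of CT rates between groups would also inherit whatever selection each group had.

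**Working it through.** The plan states no fusion rate, no X-ray accuracy and no CT result, so there is no figure of its own to reproduce. The one available check is on size: 30 patients with growing rods plus 40 with a mature skeleton (section 3.3) equals the 70 planned in section 1.3.

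**1. Fusion, under assumed accuracy.** Let p be the true fusion rate in all operated patients, and let Se and Sp be the sensitivity and specificity of the X-ray sign for CT fusion. Suppose scanning follows the sign.

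- Share scanned = p·Se + (1 − p)(1 − Sp)
- CT fusion rate among scanned = p·Se / [p·Se + (1 − p)(1 − Sp)]

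Example with p = 0.60 and Se = Sp = 0.7: 0.42 / (0.42 + 0.12) = 77.8%. The share scanned is 0.54, or 37.8 of 70.

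All values of p, Se and Sp are assumptions:

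| True rate | Se 0.7, Sp 0.5 | Se = Sp = 0.7 | Se = Sp = 0.8 | Se = Sp = 0.9 |
|---|---|---|---|---|
| 60% | 67.7% | 77.8% | 85.7% | 93.1% |
| 75% | 80.8% | 87.5% | 92.3% | 96.4% |
| 90% | 92.6% | 95.5% | 97.3% | 98.8% |

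Over Se = Sp = 0.7 to 0.9, the overstatement is 17.8 to 33.1 points at 60%, 12.5 to 21.4 points at 75% and 5.5 to 8.8 points at 90%. Between 37.8 and 57.4 of 70 patients would be scanned, and 70% to 90% of non-fused patients (the value of Sp) would not be.

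The direction does not depend on these values. The scanned rate exceeds p whenever Se > 1 − Sp. It equals p only when the X-ray is uninformative: Se = Sp = 0.5 returns 60%, 75% and 90% unchanged.

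**2. Fusion, without accuracy assumptions.** Suppose k of 70 are scanned and 95% of those are fused (illustrative). The worst case counts every unscanned patient as not fused, and the best case counts every one as fused.

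- k = 35: 33.25/70 = 47.5% to (33.25 + 35)/70 = 97.5%
- k = 50: 47.5/70 = 67.9% to (47.5 + 20)/70 = 96.4%
- k = 60: 57/70 = 81.4% to (57 + 10)/70 = 95.7%

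**3. Late screw problems.** Take p = 0.75 and Se = Sp = 0.8, so 92.3% of scanned patients are fused. Assume a 5% problem rate in fused patients and a rate s in non-fused patients, with no further link to the X-ray sign.

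- s = 15%: true 0.75×5% + 0.25×15% = 7.5%; among scanned 0.923×5% + 0.077×15% = 5.8%
- s = 30%: true 0.75×5% + 0.25×30% = 11.3%; among scanned 0.923×5% + 0.077×30% = 6.9%
- s = 5%: true 5.0%; among scanned 5.0%, so no bias

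The gap runs from zero to about 4 points and depends entirely on a link between screw problems and non-fusion that the documents do not quantify.

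**The case against.** The strongest reply is that no planned analysis is shown to be biased. Fusion and screw position are not named endpoints. Section 6 mentions no CT rate, and the one comparison it spells out concerns correction of deformity components. A scan that the protocol did not call for is arguably not missing data at all. This stands as a limit on reach: the point is conditional on a 12-month CT rate being reported. It does not remove the point, because the plan collects CT fusion findings and supplies no denominator other than the scanned patients.

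A reader might infer that the efficacy and safety conclusion as a whole is biased. The documents do not support that. The primary endpoint has no CT component, and serious adverse events are collected in all patients throughout the study (section 5). The pre-discharge CT checks early screw position without this condition. Clinically silent late screw problems could still go unseen.

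A reader might also infer that scanned patients have already been judged fused, or that the others can never be scanned. The trigger is a radiographic sign, not a verdict. Section 3.8 allows unlisted examinations at the physician's discretion, although not systematically.

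It is tempting to add that selection differs by group, since section 2 describes local fusion at the base screws in group 1 and fusion along the implants in group 2. That is possible, but the documents give no rate of bone block in either group and do not define the sign by group.

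One objection shapes the remedy. CT is optional even when the sign is present, so counting every unscanned patient as unfavourable would replace an upward bias with a downward one.

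**Conclusion.** The point holds for fusion. Any 12-month CT fusion rate with scanned patients as denominator would overstate fusion in all operated patients, provided that scanning follows the stated trigger and the X-ray carries some information about fusion. Its size cannot be derived from the documents. Under the assumed accuracies of 0.7 to 0.9 it ranges from about 5 points when true fusion is 90% to about 33 points when it is 60%. Optional non-scanning among patients with the sign, or discretionary scans outside the schedule, could change the size.

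For late screw position only a plausible direction can be claimed: it requires screw problems to be commoner without a bone block. A difference in selection between the groups is likewise unproven. The named endpoints, serious adverse event collection and early screw position are untouched by this rule. This is a reporting weakness of minor severity that can be put right cheaply.

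**What to change.** Leave the CT indication as it is and change only what is recorded and reported.

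- Record the bone-block reading of the Visit 6 X-ray for every patient. The CT trigger cannot be applied without making it.
- Report that reading by group, with all operated patients as denominator.
- Report the number scanned by group. Show *CT not done* as its own category, neither dropped as N/A nor counted as non-union.
- Label CT fusion and late screw results as applying to scanned patients only, with best-case and worst-case bounds for all operated patients as in step 2 of the working.
- State in section 6 that CT rates will not be compared between groups as if every patient had been scanned.

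The cost is one extra recorded item, a sentence in section 6 and one table. No imaging is added. The reported rates will be less favourable or have wider ranges. Because section 3.8.7 describes the X-ray only for Cobb angle and imbalance, the form needs a field for the bone-block reading.

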3.8.8. Unscheduled visits

Unscheduled visits – NMD-induced spinal deformity-related visits not required by the study protocol.

If a patient had an unscheduled follow-up visit, the data obtained during such a visit are recorded separately.

3.8.9. Study withdrawal

Patients may withdraw from the study in the following situations:

- The follow-up period has completed;
- A patient is not available to follow-up;
- Patient death;
- A patient decided to withdraw from the study (refused to continue participation, moved to a different region);
- The investigator deemed patient withdrawal from the study necessary (for example, due to medical reasons or impossibility of adequate patient compliance with protocol requirements).

If a patient is considered not available to follow-up or refuses to continue participation or the investigator deems patient withdrawal from the study necessary, the investigator shall document patient withdrawal and the reason for withdrawal. After a patient has withdrawn from the study, further data collection and additional visits are not performed.

After their withdrawal from investigation, a patient will still obtain the normal treatment comparable with that as rendered during the regular surgical correction.

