3.5. Study duration

The follow-up period for each patient will be at least 12 months. Enrollment of patients will continue for 24 months. The expected total study duration is 36 months (12 months after enrollment of the last patient).

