3.6. Inclusion/exclusion criteria

A patient should meet the inclusion criteria and lack all exclusion criteria to be considered.

Inclusion criteria:

1. Signed and dated informed consent for participation in the study (separate informed consents for child and parents/caregivers), obtained before conducting any study procedures
2. Age from 6 to 25 years

CHILDren with neuromuscular diseases – efficacy eVALuation of spinal deformity surgeRY via different pedicle screw fixation systems study
CHIVALRY study

3. Male and female patients
4. Verified and documented diagnosis with the results of neurologic examination
5. Deformity of thoracic and/or lumbar spine associated with NMD, which requires surgical intervention

Exclusion criteria:

1. Patient unwillingness or inability to follow study procedures
2. Absence of signed and dated informed consent for participation in the study (as for child and for parents/caregivers)
3. Patient participation in another clinical study, which can influence the results of this study
4. Life expectancy <12 months
5. Concomitant diseases, which preclude patient participation in this study according to doctor's opinion

Participant exclusion criteria:

Patients may be excluded from the study at any time. The reasons for exclusion may be as follows:

1. Voluntary patient withdrawal (consent withdrawal for any reason or without giving a reason) without negative effects on further treatment.
2. Failure to follow-up a patient.

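### Section 3.8.9 ends data collection for every withdrawn patient without separating leaving study procedures from withdrawing consent, which permits avoidable loss of 12-month outcomes after surgery

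*Combined protocol and SAP*

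**What the plan says.** Section 3.8.9 lists the situations in which a patient leaves the study: completed follow-up, unavailability, death, the patient's own decision (refusal or relocation), and the investigator's decision. The last is worded: "The investigator deemed patient withdrawal from the study necessary (for example, due to medical reasons or impossibility of adequate patient compliance with protocol requirements". The examples are open-ended, and nothing limits this ground to the time before surgery. The reason for withdrawal must be documented. The section then applies one consequence to all: "After a patient has withdrawn from the study, further data collection and additional visits are not performed".

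Section 3.6 has its own, shorter list of reasons for removing a participant: "Voluntary patient withdrawal (consent withdrawal for any reason or without giving a reason) without negative effects on further treatment" and "Failure to follow-up a patient". Non-compliance appears there only as an entry exclusion: "Patient unwillingness or inability to follow study procedures".

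The primary endpoint in section 3.2 is "decrease in spine deformity grade by 1 or more (according to Chaklin classification) with stabilization or improvement in lung parameters in 12 months" after surgery. Section 3.5 says: "The follow-up period for each patient will be at least 12 months". On incomplete data, section 6 says: "Missing data will be indicated as N/A and not considered in aggregate statistics".

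Section 5 first ends follow-up of a serious adverse event at resolution, withdrawal or study completion, whichever comes first. It then says that if a patient withdraws early, every effort is made to keep following the event.

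**The concern.** Surgery takes place at Visit 2, and the visit schedule lists only assessments after it. A medical problem, poor compliance or a move to another region is therefore not in itself a reason to give up the 12-month X-ray and scales of an operated patient who has not refused them. Yet 3.8.9, read literally, stops their collection.

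The grounds for withdrawal are also unlikely to be neutral. Medical reasons after spinal surgery in children with neuromuscular disease could include complications or respiratory decline, and the primary endpoint itself requires lung parameters to be at least stable. A ground for removal can thus overlap with failure on the endpoint. The study is open, single-centre and non-randomised, so no randomised control group shares the same loss. At stake is a success rate that is too high because patients with a poor course are not observed at 12 months and then leave the denominator.

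**Working it through.** **Step 1. Routes out of the study, side by side.**

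| Route in 3.8.9 | Among the removal reasons in 3.6? | Consent to data withdrawn? | Further data under 3.8.9 |
|---|---|---|---|
| Follow-up completed | No | No | None due |
| Unavailable | Yes | Not stated | Stopped |
| Death | No | Not applicable | None possible |
| Patient refuses | Yes | Possibly; not distinguished | Stopped |
| Patient moves away | Not separately | Not necessarily | Stopped |
| Investigator decides | No | Not necessarily | Stopped |

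The last two rows, and any patient classed as unavailable who later proves reachable, are where loss is avoidable.

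**Step 2. What is lost.** The primary endpoint is defined at 12 months, so Visit 6 is its only reading. An operated patient withdrawn earlier contributes neither the 12-month deformity grade nor the 12-month scales.

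**Step 3. What the analysis does with it.** Section 6 omits missing values from aggregate statistics, so the reported rate is the rate among patients kept.

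**Step 4. Illustration.** The plan states no success rate, withdrawal rate or dropout allowance, so there is no figure of its own to reproduce beyond 30 + 40 = 70 patients. The inputs below are assumptions: success of 70% in patients kept and 30% in patients lost, with a share *d* lost.

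Rate in all operated patients = (1 − d) × 0.70 + d × 0.30. Overstatement = 0.70 minus that rate = 0.40 × d.

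| d | About, of 70 | Rate in all operated | Reported | Overstatement |
|---|---|---|---|---|
| 5% | 4 | 0.95 × 0.70 + 0.05 × 0.30 = 68% | 70% | 2 points |
| 10% | 7 | 0.90 × 0.70 + 0.10 × 0.30 = 66% | 70% | 4 points |
| 20% | 14 | 0.80 × 0.70 + 0.20 × 0.30 = 62% | 70% | 8 points |

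These figures pool everyone lost without withdrawing consent. If none of them was reachable, this rule causes none of the overstatement. If all were reachable and consenting, it causes all of it.

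**Step 5. Extreme case.** Suppose every lost patient is a failure.
- Assumed true rate 60% (42 of 70): reported 42/66 = 63.6%, 42/63 = 66.7% or 42/56 = 75.0%.
- Assumed true rate 80% (56 of 70): reported 56/66 = 84.8%, 56/63 = 88.9% or 56/56 = 100%.

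The bias then runs from about 4 to 20 points. The distance between best-case and worst-case results is the share lost: 4/70 = 5.7, 7/70 = 10 and 14/70 = 20 points.

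**Step 6. Section 3.8.9 against section 5.** Section 3.8.9 stops data collection at withdrawal. Section 5 both ends event follow-up at withdrawal and promises to continue it beyond withdrawal. These statements cannot all be followed.

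**The case against.** Several stronger readings are tempting, and the documents do not support them.

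- *All data stop at withdrawal.* Section 5 promises continued follow-up of serious adverse events. The stop is unqualified for efficacy data; for safety data the documents contradict themselves.
- *Sections 3.6 and 3.8.9 contradict each other.* The list in 3.6 is introduced permissively and need not be exhaustive. The mismatch is untidy drafting, and the point does not depend on it.
- *Missing Visit 5 forfeits Visit 6.* Nothing says that one missed visit makes a patient unavailable, or that this status is permanent. The text leaves it open.
- *Loss is built in, or the operating team removes patients who do badly.* No withdrawal frequency is given, reasons must be recorded, and participation starts at consent, so the investigator ground has an ordinary use before surgery. The rule permits selective loss; it does not show that it happens.
- *Nothing remains to be done after surgery.* The schedule lists only assessments, but the documents do not say whether the growing rods in group 1 (30 of 70) are lengthened later.
- *No analysis could help.* Counting withdrawn patients as failures, or giving best-case and worst-case limits, would bound the result. It would not supply the unobserved outcomes.
- *Better retention secures the primary endpoint.* Spirometry at Visit 6 is done only where medically indicated (Table 1 and section 3.8.7). Even a fully retained patient may lack the lung component.

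What stands is that 3.8.9 does not separate leaving study procedures from withdrawing consent to data, and that consenting, reachable patients can lose their 12-month assessments as a result.

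**Conclusion.** The point holds as a permitted, avoidable weakness in data collection, and it should be corrected. For operated patients, 3.8.9 allows 12-month assessments to be lost for reasons plausibly related to outcome, and section 6 then drops those patients from the summaries. The direction is probably towards too favourable a result, on the assumption that withdrawn patients fare worse than those kept.

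The size cannot be known from the documents. The 2 to 8 points are illustrative, and the share due to this rule lies anywhere between none and all of them, depending on how many lost patients were reachable and still consenting. Separately from any figure, 3.8.9 and section 5 conflict on follow-up of serious adverse events and must be reconciled.

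**What to change.** Replace the sentence in 3.8.9 that stops data collection with:

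> Unless consent is withdrawn, the scheduled Visit 6 assessments (X-ray, functional and quality-of-life scales, SAE documentation, and spirometry where it is performed under the protocol) are sought for every operated patient, whatever the reason for leaving other study procedures and including those who missed Visit 5; an X-ray done locally is accepted. A patient is classed as lost only after the Visit 6 window closes. Data up to withdrawal of consent are kept.

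The Visit 6 window closes at 12 months plus 30 days (Table 1). Align the lists in 3.6 and 3.8.9, and reconcile both with the SAE follow-up text in section 5.

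The cost is protocol wording, some contact effort and a few X-rays from outside the centre. The wording adds no test, since it covers only assessments already scheduled and leaves spirometry as the protocol has it. The optional status of Visit 6 spirometry is a separate limit on the primary endpoint, which this change does not resolve.
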